13.4 Analysis of Secondary Endpoints

Overall survival is defined as the duration of time from date of randomization to time of death. Subjects lost to follow-up or whose vital status is unknown, will be right-censored at the date the subject was last known to be alive. Every effort will be made to determine outcome, including phone calls, certified mail, and the checking of public records as necessary. The evaluable population is as defined for the primary endpoint. Results will be summarized descriptively using Kaplan-Meier plots, and compared between groups, under the assumption of proportional hazards, using the stratified log-rank test to account for tumor site.

The density of CD8+ T cells in each treatment group, at baseline and after treatment, will be visualized using boxplots, and described using summary statistics including means and s.d. presented with 95% confidence intervals. A student t-test or nonparametric Wilcoxon rank-sum test will be used to determine whether the increase in CD8+ T cells is greater in treatment arm B (combination cobimetinib plus atezolizumab) than in treatment arm A (atezolizumab monotherapy).

13.5 Reporting and Exclusions

13.5.1 Evaluation of Toxicity

The safety analysis will be performed in all subjects who receive any amount of study drug. A baseline measurement and at least 1 laboratory or other safety-related measurement obtained after at least 1 dose of study treatment may be required for inclusion in the analysis of a specific safety parameter (e.g., lab shifts from baseline). A complete list of all AE data will be provided along with an assessment of NCI CTCAE version 5.0 grade and relationship to study drug. The incidence of AEs will be tabulated by subgroups of interest (e.g. grade 3 or higher, organ class, relationship to study drug). For analyses at the individual level, the highest grade and relationship to study drug will be assumed if multiple events have occurred. Toxicity will be tabulated by type and grade and will be summarized with descriptive statistics. Other safety data will be assessed in terms of physical examination, clinical chemistry, hematology, vital signs, and ECGs. Negative binomial regression and Cox proportional hazards models will be used to assess the rate of AE and time to first toxicity, respectively.

13.5.2 Evaluation of Response

All subjects who have completed at least one dose of therapy will be included in the evaluation of response. Each patient will be assigned of the following categories: 1) complete response, 2) partial response, 3) stable disease, 4) progressive disease, 5) early death from malignant disease, 6) early death from toxicity, 7) early death because of other cause, or 9) unknown (not assessable, insufficient data).

The objective response rate is defined as the proportion of response evaluable subjects who have a complete response (CR) or partial response (PR) using RECIST 1.1 criteria at any time during the study. The evaluable population is as defined for the primary

endpoint. Response rates will be reported for each group along with exact confidence intervals, and an exact binomial test will be used to compare response rates across treatment groups.

Evaluation of Correlative Aims

Correlative studies will be performed:

- To measure the baseline expression and on treatment expression of PD-L1 and correlate these variables with treatment response.
- To measure the baseline levels of immune markers including CD8+ T effector cells and CD4+FoxP3+ T regulatory cells, and tumor infiltrating lymphocytes (TILs), major histocompatibility complex (MHC) class I and II expression, and natural killer (NK) cell receptors and ligands expression and correlate these variables with treatment response and toxicity.
- To characterize changes in the immune markers described above after treatment
- To measure changes in circulating immune suppressor cells (MDSC, Treg) in peripheral blood by flow cytometry and test for association with response to therapy.

The overarching aim of these studies is to establish baseline levels for, and measure changes in immunological pathways after treatment. Little is known about baseline levels for these variables in cholangiocarcinoma, let alone changes after treatment, and if the primary and secondary aims are successful, these investigations will establish a biological foundation on which to build in follow up studies.

Immunological variables will be examined in plots and summary statistics, to characterize distributions, identify outliers and other potential problems in the data. Joint exploratory analysis will identify associations and potential interactions. Variables may be transformed on the basis of these investigations, to reduce skewness, minimize the influence of outliers and/or to regularize relationships between predictors and response for better model fit. Exploratory analysis of the molecular markers, including visualizations and statistical summaries such as hierarchical cluster analysis, heat maps, multidimensional scaling, and principle component analysis will offer important views of the structural characteristics of the expression data.

Response will be described categorically, and associations between response and immunological variables will be characterized, in each arm, using multivariate logistic regression models, with adjustment for clinical and pathological co-variates that may be associated with response. Estimated effects will be reported with standard errors and confidence intervals.

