11.1.1 Definitions

Evaluable for toxicity. All patients will be evaluable for toxicity from the time of their first treatment with cobimetinib or atezolizumab.

Evaluable for objective response. Only those patients who have measurable disease present at baseline, have received at least one cycle of therapy, and have had their disease re-evaluated will be considered evaluable for response. These patients will have their response classified according to the definitions stated below. (Note: Patients who exhibit objective disease progression prior to the end of cycle 1 will also be considered evaluable.)

Evaluable Non-Target Disease Response. Patients who have lesions present at baseline that are evaluable but do not meet the definitions of measurable disease, have received at least one cycle of therapy, and have had their disease re-evaluated will be considered evaluable for non-target disease. The response assessment is based on the presence, absence, or unequivocal progression of the lesions.

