13. STATISTICAL CONSIDERATIONS

13.1 Study Design/Endpoints

The proposed study is an open-label, randomized phase 2 multicenter trial evaluating cobimetinib in combination with atezolizumab compared with atezolizumab monotherapy in unresectable cholangiocarcinoma.

The primary clinical endpoint is progression free survival and the primary objective of the trial is to determine whether the combination of cobimetinib in combination with atezolizumab yields a clinically compelling antitumor activity measured as progression free survival (PFS). Additional secondary endpoints include safety, objective response rate (ORR, assessed by RECIST 1.1), overall survival (OS), and other immunologic correlates.

The principle correlative objective of the trial is to determine whether the combination of cobimetinib and atezolizumab increases immune response compared to atezolizumab monotherapy. The change CD8+ density within tumor after 21 days of treatment, as compared to baseline, is an integrated biomarker for this clinical trial.

The study is planned with 76 evaluable subjects (38 subjects per treatment arm), to achieve 90% power using a 1-sided test with alpha=0.05. Both of these drugs are in common use and will be given at full dose. The combination of cobimetinib and atezolizumab was previously tested, and well tolerated in a similar population of patients with metastatic colorectal cancer, so unacceptable rates of toxicity are not expected, but the present study will be continuously monitored for adverse events. The primary study team made up of the study PI [name], [REDACTED] Dr. [REDACTED], and lead study nurse and coordinator at the lead site Johns Hopkins will meet weekly to discuss adverse events. In addition, the primary study team will have bimonthly calls with representatives at all the enrolling sites to monitor toxicity continuously.

Progression-free survival is defined as the duration of time from date of randomization to time of progression or death. The evaluable population includes all subjects who have completed at least one dose of therapy and have received at least one follow-up scan. Patients who come off of study treatment for clinical progression prior to the first follow-up scan (i.e. clinical progression)

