will also be considered evaluable and will be coded as progressors for the analysis. Due to the rapid progression of the disease in the majority of patients, little loss to follow up is expected, but subjects who are lost to follow-up as of the data analysis cutoff date will be right-censored. The censoring date will be determined from the date the subject was last evaluated for progression. PFS within each treatment arm will be summarized descriptively using Kaplan-Meier plots, and compared between groups, under the assumption of Cox proportional hazards, using the stratified log-rank test to account for tumor site. An interim analysis will be conducted when half the required PFS events have been observed (35). The trial will be stopped early for futility if the p-value from the log-rank statistic is greater than 0.5 (i.e., the PFS is worse for study arm B than for study arm A).

The analysis will be stratified on site of disease (gallbladder cancer, intrahepatic cholangiocarcinoma, and extrahepatic cholangiocarcinoma). An interim analysis will be conducted when half the required PFS events have been seen (35), and the trial will be stopped early for futility if median PFS is lower by any amount, under the combination therapy than under monotherapy.

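### Section 13.5.2 does not fix one objective response rate: its denominator, response window and two-arm test conflict with, or are left open against, sections 13.1, 11.1.1 and 11.1.4.3

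*Combined protocol and SAP*

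**What the plan says.** ORR is a secondary objective (1.2.2). Four sections bear on it.

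- **13.5.2, opening:** "All subjects who have completed at least one dose of therapy will be included in the evaluation of response". The category list provides for early death from disease, toxicity or other cause, and for unknown.
- **13.5.2, ORR paragraph:** the rate is a proportion of response-evaluable subjects, and "The evaluable population is as defined for the primary" endpoint. Section 13.1 defines that set: "The evaluable population includes all subjects who have completed at least one dose of therapy and have received at least one follow-up scan". Patients who stop for clinical progression before the first scan "will also be considered evaluable and will be coded as progressors for the analysis".
- **11.1.1:** evaluable for response are "Only those patients who have measurable disease present at baseline, have received at least one cycle of therapy, and have had their disease re-evaluated". One exception is noted: "Patients who exhibit objective disease progression prior to the end of cycle 1 will also be considered evaluable".
- **Numerator, 13.5.2:** patients with a complete response ("CR) or partial response (PR) using RECIST 1.1 criteria at any time during the study"). Section 11.1.4.3 closes the window for best overall response at progression or recurrence and makes the assignment depend on confirmation as well as measurement.
- **Test, 13.5.2:** "an exact binomial test will be used to compare response rates across treatment groups". No null value, alpha or sidedness is given for ORR. A one-sided 5% level is stated for PFS (13.1, 13.2) and for the CD8+ t-test (13.2).

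**The concern.** Two analysts who both follow the text could report different response rates and p-values from the same data.

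The scan requirement also works in one direction within an arm. A treated patient who leaves before any scan, without clinical progression, cannot be a responder. Removing that patient shrinks the denominator and leaves the numerator alone.

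The numerator wording reaches past progression. By 5.4 and 5.5 a patient remains on study, with disease status monitored, until death, withdrawal or closure, and 5.3.1 allows treatment beyond progression in both arms.

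The name of the test, taken at face value, describes a procedure that treats one arm's rate as known.

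Response is also the outcome in the correlative logistic models of 13.5.2, so an unsettled definition carries into those analyses.

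**Working it through.** The plan gives no power, sample size or alpha for ORR, so there is no ORR figure to reproduce.

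**1. Denominator: the three sets applied to three patients**

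| Patient | 13.5.2 opening | 13.1 set | 11.1.1 set |
|---|---|---|---|
| One dose, toxic death before first scan, no clinical progression | in | out | out |
| Stops for clinical progression before first scan, no re-evaluation | in | in | out (only objective progression is excepted) |
| Stops in cycle 1 for toxicity, scanned at week 8 | in | in | out (less than one cycle) |

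Inputs for size: about 82 enrolled (13.2), so 82/2 = 41 per arm if split equally; 76 evaluable, 38 per arm (13.1). Assumptions: six responders in an arm, and 0 to 3 of the 41 − 38 = 3 patients lost per arm were treated non-responders. Section 4.4 recognises that some registered patients may never be dosed; those are in neither set.

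- 13.1 set: 6/38 = 15.8%, exact (Clopper-Pearson) 95% CI 6.0% to 31.3%.
- All treated, if all three were dosed: 6/41 = 14.6%, CI 5.6% to 29.2%.
- Difference: at most 15.8 − 14.6 = 1.2 points, against an interval 31.3 − 6.0 = 25.3 points wide.

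**2. Numerator**

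The time windows differ outright: end of study in 13.5.2, progression or recurrence in 11.1.4.3. On confirmation, 13.5.2 is silent rather than contradictory. The text of 11.1.4.3 reads as requiring it, although its table column is headed as applying only where confirmation is required. Each response counted under one reading and not the other moves an arm by 1/38 = 2.6 points.

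Section 11.1.6 matters here. For a patient treated beyond progression whose next scan does not show progression, PFS progression is dated to a later scan that does. A response after such an unconfirmed first progression therefore falls before the PFS progression date.

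**3. Test**

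Notation: *a* and *b* responders of 38 in Arms A and B.

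- Literal one-sample reading: p = P(X ≥ b), with X ~ Binomial(38, a/38).
- Fisher one-sided: p = P(H ≥ b), with H hypergeometric given a + b total responders. Fisher two-sided sums the tables no more likely than the one observed.
- Type I error at common rate π: the sum over all (a, b) of Bin(a; 38, π) × Bin(b; 38, π) for tables with p ≤ 0.05.

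Results at nominal one-sided 5%, π = 10%:

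- One-sample test against Arm A's observed rate: 13.5%.
- Fisher: 1.8%.

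In the one-sample figure, a = 0 with b > 0 counts as rejection. Those tables contribute 0.9^38 × (1 − 0.9^38) = 0.0183 × 0.9817 = 1.8 points, so the excess does not rest on them. Over common rates of 5% to 25%, the one-sample error runs from 11.5% to 16.8%; Fisher stays at or below 3.0%.

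Illustration, 2/38 against 8/38 (assumed counts):

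| Test | p |
|---|---|
| One-sample, one-sided | 0.0007 |
| Fisher, one-sided | 0.043 |
| Fisher, two-sided | 0.086 |

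**The case against.** **The opening sentence of 13.5.2 may only say who is classified.** The ORR paragraph then names its own denominator. That is a fair reading, and it removes the conflict inside 13.5.2. It leaves 13.1 against 11.1.1, and it leaves the upward effect of the scan rule.

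**The categories do not prove absence of a scan.** A reader might infer that every patient classed as toxic death, other early death or unknown has no scan and is dropped. The documents do not say so: an early death can follow a scan, and an unknown can be a scanned patient whose images were not assessable. Only patients with neither scan nor clinical progression leave the set.

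**The numerator is less open than it looks.** Section 13.5.2 invokes RECIST 1.1, which section 11 details, and 11.1.4.3 reads as requiring confirmation. This stands for confirmation. It does not cure the different time window, because 13.5.2 never refers to 11.1.4.3.

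**A comparison across groups plainly means a two-sample test.** Probably so. A reader might infer that the plan intends the invalid one-sample test; the text does not show that, only that its wording permits it. The illustration was also chosen near 0.05: Fisher is non-significant either way at 3/38 against 8/38 (one-sided 0.095) and significant either way at 2/38 against 9/38 (two-sided 0.047). The plan sets no alpha for ORR, so any threshold here is supplied by the reader. The choice among valid two-sample exact tests is largely preference; the missing sidedness is not.

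**Conclusion.** The point holds, at minor to moderate severity. The text leaves ORR undetermined in its denominator, its response window and its test.

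- **Denominator:** the scan rule can only raise ORR, by at most about 1.2 points under the assumed six responders and three treated non-responders lost per arm.
- **Window:** 2.6 points per affected response. How many there would be is unknown.
- **Test:** about 13.5% type I error if the name is taken literally (10% in both arms, 38 per arm), against 1.8% for Fisher. Sidedness alone can change the conclusion in the illustrated case.

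A reader might infer that the scan rule favours one arm. Nothing in the documents shows this: the rule applies to both arms, and early losses by arm are not given. Nor does the point reach the primary result: ORR is secondary and unpowered, and the PFS design and analysis do not depend on it.

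**What to change.** 1. **Denominator.** In 13.5.2, use all patients with at least one dose and count everyone without CR or PR as a non-responder. Make 11.1.1 refer to this set. The 13.1 evaluable set can be kept as a supportive analysis.
2. **Numerator.** Define ORR as best overall response of CR or PR under 11.1.4.3, with confirmation at 4 weeks or more as that section reads. Date progression by the PFS rule in 11.1.6, so that ORR and PFS agree for patients treated beyond progression. Cutting ORR at the first progression on any scan would create a new mismatch with PFS. Report unconfirmed ORR as supportive. Exclude responses after other anticancer therapy only where its start date is recorded: concomitant therapy is captured to the treatment discontinuation visit (5.2.1), and no section shows later therapy dates being collected.
3. **Test.** Replace the exact binomial test with a named two-sample exact test such as Fisher's, and state its sidedness, for example one-sided 5% as for PFS.

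**Cost.** Wording in 13.5.2 and 11.1.1; no extra patients or visits, and 8-weekly scans already allow confirmation. Reported ORR will be slightly lower, and ORR will sit on a different set from PFS and OS. Some responses after progression will not be counted. They may not reappear under irRC either, because irPR needs a confirmed fall of at least 50% in bidimensional tumor burden (Appendix D), against 30% in summed diameters for a RECIST PR (11.1.4.1).

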1.2 Secondary Objectives

- 1.2.1 To assess the overall survival (OS) of patients receiving cobimetinib in combination with atezolizumab and atezolizumab monotherapy for unresectable cholangiocarcinoma.
- 1.2.2 To determine the objective response rate (ORR), defined as complete plus partial response, of cobimetinib in combination with atezolizumab and atezolizumab monotherapy in patients with unresectable cholangiocarcinoma.
- 1.2.3 To assess the safety and tolerability of cobimetinib in combination with atezolizumab and atezolizumab monotherapy in patients with unresectable cholangiocarcinoma.
- 1.2.4 To determine the relationship between PD-L1 expression in tumor at baseline and on treatment, and response to treatment.

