9.3.2.3 Shipping of Tumor Specimens

- Tissue samples (archival and fresh tumor biopsies) should be shipped to JHU biannually. Tissues for correlative research studies will be shipped from each institution to [name] at Johns Hopkins University, for analysis of integrated (CD8+, PD-L1 staining) and exploratory biomarkers outlined below. Please call ahead or email ([contact], [REDACTED], and [REDACTED]) to alert us of shipment with tracking number if available. To ensure the integrity of tissue specimens, shipment should occur on Monday-Wednesday to avoid unanticipated delivery delay due to weekends or holidays.
- Frozen tissue samples must be shipped frozen and maintained in the frozen state. All shipments should be made in freezer boxes containing DRY ICE, and labeled as HUMAN SAMPLES: NONINFECTIOUS.
- Each tumor sample must be clearly labelled with the study number (10139), the subject's ID, the date and time of collection, tissue biopsy site (i.e. liver), the study time point (i.e. BL, C1D21), and the tissue type (i.e. frozen RNA Later)

The shipping address for **Tissue Samples (NOT RESEARCH BLOODS)** is as follows:

[REDACTED]
Attn: NCI 10139
[name]
CRBI Room [REDACTED]
[name]

3. Immunohistochemical analysis of tumor tissue

Paired tumor biopsies will be used to assess the effect of treatment arm on changes in the TME. This analysis will be performed on paired samples from patients enrolled in the trial. Baseline pretreatment biopsies, when available, will be collected. In addition, specimens from the on-treatment biopsy will be collected under the guidance of the collaborating pathologist and tissue procurement staff at the time of biopsy.

Our study design will enable us to isolate the effect of each treatment arm treatment combinations on immune cells, and other biomarkers in the TME in the context of atezolizumab +/- cobimetinib. For the integrated biomarker of CD8+ staining, IHC assays will be conducted in a Central Reference CLIA Laboratory using the Cell Marque, CD8 (C8/144B), mouse monoclonal antibody, Ref#108M-98, Status IVD. Further technical details for this biomarker are listed in appendix C. PD-L1 expression will be another integrated biomarker and will be conducted in a Reference CLIA Laboratory.

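### Section 13.5.2 lets marker scales be chosen by their fit to response and then reports unadjusted intervals. This is also the only analysis of secondary objective 1.2.4, so PD-L1 associations may be overstated.

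*Combined protocol and SAP*

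**What the plan says.** The part of section 13.5.2 on correlative aims sets out a sequence. First comes a data-driven look: "Joint exploratory analysis will identify associations and potential interactions". Then "Variables may be transformed on the basis of these investigations, to reduce skewness, minimize the influence of outliers", with a third and/or reason, "to regularize relationships between predictors and response for better model fit". Response is then modelled "in each arm, using multivariate logistic regression models, with adjustment for clinical and pathological co-variates that may be associated with response". Finally, "Estimated effects will be reported with standard errors and confidence intervals".

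The section lists no transformations and no covariates. It describes no validation, shrinkage or allowance for having selected a scale, and it does not state the confidence level or the type of interval.

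PD-L1 falls under this text. Secondary objective 1.2.4 is "To determine the relationship between PD-L1 expression in tumor at baseline and on treatment, and response to treatment", and the heading on immunohistochemical analysis within section 9.3.2.3 states that "PD-L1 expression will be another integrated biomarker". Section 13.4, on secondary endpoints, covers overall survival and CD8 density but not PD-L1. The only analysis entry for PD-L1 is the correlative aim in section 13.5.2: "To measure the baseline expression and on treatment expression of PD-L1 and correlate these variables with treatment response".

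**The concern.** Transforming a marker because it is skewed or has outliers uses the marker values alone and does not bias its association with response. Choosing the scale on which the marker best tracks response uses the outcome. If the same patients then supply the estimate and its interval, the estimate tends to lie further from zero than it would on a scale fixed beforehand, and the interval takes no account of the search.

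At stake is how far the marker-response estimates can be trusted when they are carried into later studies, which section 13.5.2 names as their use. For most of the markers that is an accepted feature of exploratory work. PD-L1 is different because its relation to response is a numbered secondary objective.

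**Working it through.** **The plan's own figures.** The documents give no power or error rate for the marker-response models. The nearest figure is the CD8 power statement in section 13.2, which also supplies the number of paired biopsies. With 20 per arm, a one-sided 5% t-test and noncentrality d × √(20/2), a difference of 0.8 SD gives 2.53 and power 79.9%, and 1.0 SD gives 3.16 and power 92.8%. The stated 80% and more than 90% are reproduced.

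**Inputs from the documents.** There are 38 evaluable patients per arm (13.1) and about 20 per arm with paired biopsies (13.2). Models are fitted separately in each arm (13.5.2). Section 2.3 quotes 4/23 = 17% response for another checkpoint inhibitor in PD-L1-positive disease.

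**Assumptions.** Response is 17% or 30%. The marker is log-normal and unrelated to response. There are no covariates, and intervals are 95%. Candidate scales are raw, log, square root and rank, with a median split as an optional fifth. Datasets with fewer than two responders or two non-responders are dropped.

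**Method.** In each simulated arm, fit logit P(response) = a + b·T(x), with T(x) scaled to unit SD. Keep the T with the highest likelihood. Count a false positive by the likelihood-ratio test if 2(ll₁ − ll₀) > 3.84, and by the SE-based (Wald) interval if |b/SE| > 1.96. The comparator is a log scale fixed in advance.

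**False-positive rates (%).** The likelihood-ratio columns come from 4,000 datasets per row. The Wald columns come from a separate run of the same setup with about 3,500-4,000 usable datasets.

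| Patients, response | LR: fixed log | LR: best of 4 | LR: plus median split | Wald: fixed log | Wald: best of 4 | Wald: plus median split |
|---|---|---|---|---|---|---|
| 20, 17% | 7.6 | 10.7 | 15.3 | 0.6 | 0.7 | 0.6 |
| 20, 30% | 6.4 | 10.3 | 13.6 | 2.1 | 2.3 | 2.9 |
| 38, 17% | 5.9 | 9.5 | 12.1 | 3.3 | 3.8 | 3.9 |
| 38, 30% | 6.4 | 10.2 | 12.4 | 4.4 | 5.3 | 7.2 |

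A repeat of the four-scale comparison gave likelihood-ratio rates of 5.7-7.7% with a fixed log and 8.9-11.5% for the best of four, with Wald rates of 0.8-4.3% throughout. The single 5.3% is within simulation error of 5%: √(0.05 × 0.95/4,000) = 0.34 points. A larger check of that row with 20,000 datasets gave 4.7%.

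**Size of the estimate.** This does not depend on the type of interval. At 38 patients and 17% response with no true effect, the median |log OR| per SD is 0.31 with a fixed log and 0.47 for the best of four, and 0.47/0.31 = 1.52. Across the four settings the increase is about 45-55%. With a true log OR of 0.5 per SD of the log marker, the median estimate is 0.52 with a fixed log. It is 0.55 for the best of three continuous scales, 0.59 for the best of five, and 0.78 if quartile and median cut-points are also tried.

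**Why the two interval types differ.** Expected responders per arm are 20 × 0.17 = 3.4 and 38 × 0.17 = 6.5. With so few, a large estimate brings a large standard error, so Wald intervals are conservative to begin with. Selection uses up part of that slack.

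**The case against.** The strongest reply has four parts.

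1. **The wording is permissive.** Variables may be transformed, and two of the three reasons do not involve response. This stands. A reader might infer that scales will be chosen on response and that associations are therefore overstated. The text supports only that they may be.

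2. **No test is named.** Section 13.5.2 promises standard errors and confidence intervals, most naturally read as Wald intervals, and these stay at or below about 5% with continuous scales. This also stands. A reader might infer that intervals are generally too narrow and false positives well above nominal. That holds only for likelihood-type intervals or, for Wald intervals, in some settings once cut-points are allowed. The clause does not mention cut-points, and Appendix C commits CD8 change to a continuous scale. Nothing equivalent is said for PD-L1. The rise in the point estimate remains under either interval.

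3. **The work is exploratory.** Section 13.5.2 describes the aim as establishing baseline levels and changes, and sections 2.4 and 9.1 include PD-L1 expression in the exploratory rationale. This answers the point for the exploratory markers. It does not answer it for PD-L1, which is also a secondary objective and an integrated biomarker.

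4. **Sparse data are the larger problem.** Three to six responders per arm with unlisted covariates is a separate weakness that fixing the scale leaves in place. That is true, but it is no reason to keep a clause that adds bias.

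**Conclusion.** The point holds in a limited form. The plan states a rule under which the scale of a marker may be chosen by its fit to response and the effect then reported without adjustment, and that rule governs the only analysis of secondary objective 1.2.4. If it is used with four continuous scales, expect estimates with no true effect to be about half as large again, and likelihood-ratio error of 9-12% where a fixed scale gives 6-8%. SE-based intervals exceed 5% only with a cut-point, at about 7% for 38 patients and 30% response.

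These sizes rest on the assumed marker distribution, response rates, candidate scales and absence of covariates, none of which the plan fixes. A reader might go further and conclude that the trial's result is at risk. The documents do not support that: PFS is compared by a stratified log-rank test, CD8 change between arms by a t-test or rank-sum test, and no stopping or success rule uses these models. This is an improvement worth making at almost no cost, not a flaw in the design.

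**What to change.** For PD-L1, delete the and/or reason "to regularize relationships between predictors and response for better model fit" and add a sentence along these lines: *The analysis scale for PD-L1 will be chosen from the marker distribution alone, masked to response and treatment arm, and fixed before any model with response is fitted.*

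For the other markers, either apply the same rule or label any response-guided scale as post hoc and its interval as exploratory and unadjusted for selection.

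Fixing the scale returns the likelihood-ratio rate to about 6-8%; the remaining excess is a small-sample effect. A fixed scale that is not the true one costs little: with the scale fixed at log and a true effect of 0.5 on the raw scale, the estimate was 0.47. The change costs one or two sentences in section 13.5.2, with no added data, patients or assays.
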